5.5. Adjustments for Covariates

Statistical modeling of data using covariates is not anticipated in this study. However, such modeling may be performed as post hoc analyses if deemed appropriate.

5.6. Handling of Dropouts or Missing Data

Last-observation-carried-forward (LOCF) will be used in handling of missing data when it is applicable. For those patients who are lost to follow-up, or who drop out of the study, the analyses will include all data up to the point of their last data collection.

5.7. Multicenter Studies

Statistical modeling of data using country or site as covariates is not anticipated in this study. However, such modeling may be performed as post hoc analyses if deemed appropriate.

5.8. Patient Disposition

The number and percentage of GMB-treated patients who discontinue early will be tabulated along with reasons for discontinuation.

Patient allocation and reasons for discontinuation by investigator will also be listed.

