3.1. Study Rationale

Study CGAR is a Phase 3b study to assess the long-term safety and tolerability of galcanezumab 300 mg in patients with episodic or chronic cluster headache who have completed one of the Phase 3 double-blind, placebo-controlled studies, CGAL or CGAM.

Study CGAR will implement a dosing strategy to more closely approximate what may occur in clinical practice. For each patient, the study investigator will determine whether or not to dose galcanezumab 300 mg at each monthly interval based on clinical symptoms and response. Dosing will be no more frequent than once per month, and the investigator may choose to not dose galcanezumab for 1 or more months at their clinical discretion based on clinical efficacy. As such, some patients may receive monthly long-term treatment with galcanezumab for a period of months or years during the study, while others may have 1 or more months of galcanezumab dose-free intervals based on the investigator's judgment of clinical efficacy.

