3.3. Benefit/Risk Assessment

More information about the known and expected benefits, risks, and reasonably anticipated AEs of galcanezumab may be found in the IB. Information on AEs expected to be related to the investigational product may be found in Section 7 (Development Core Safety Information) of the IB. Information on SAEs expected in the study population independent of drug exposure and that will be assessed by the sponsor in aggregate periodically during the course of the study, may be found in Section 6 (Effects in Humans) of the IB.

4. Objectives and Endpoints

Table 4.1 shows the objectives and endpoints of the study.

Table 4.1. Objectives and Endpoints

Objectives	Endpoints

Primary To evaluate the safety of open-label galcanezumab within the context of expected medical practice in eligible patients with episodic or chronic cluster headache.
	
Analysis of:
 
 • TEAEs • SAEs • Suicidal ideation and behaviors assessed by solicited questioning using the C-SSRS

Secondary To characterize the reasons for discontinuation and AEs of interest for galcanezumab. To characterize the immunogenicity of galcanezumab.
	
Discontinuation rates
 
Analysis of:
 
 • Injection-site reactions • Allergy/hypersensitivity • Infections • The development and consequences of ADAs to galcanezumab, their relationship with AEs, and neutralizing ADAs to galcanezumab

Tertiary To evaluate the effectiveness of galcanezumab. To evaluate the effect of galcanezumab on health values.
	
 • The proportion of patients reporting a score of 1 (“very much better”) or 2 (“much better”) on the PGI-I 1 month after receiving their first dose will be reported. 
EQ-5D-5L Analysis of:
 
 • Health state index values • Each dimension of the descriptive system and dichotomized level responses • EQ-VAS current health score • Correlations with PGI-I, cluster headache status

Abbreviations: ADA = anti-drug antibodies; C-SSRS = Columbia-Suicide Severity Rating Scale; EQ-5D-5L Analysis = European quality 5-dimensions 5-levels; EQ-VAS = European Quality Visual Analogue Scale; PGI-I = Patient Global Impression of Improvement; SAE = serious adverse event; TEAE = treatment-emergent adverse event.

5. Study Design

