5.1. Overall Design

Study CGAR is a Phase 3b single-arm, open-label safety study of galcanezumab 300 mg in outpatients with episodic or chronic cluster headache who completed Study CGAL or Study CGAM.

Please refer to the Protocol Operations Manual for information regarding the schedule of activities, study design, study tools, and patient scenario examples.

The study will consist of 2 SP:

- SP I is the screening phase to confirm patients meet the inclusion/exclusion criteria.
- SP II is the open-label treatment phase during which patients can receive galcanezumab 300 mg administered subcutaneously (SC) up to once a month.

Study Phase I: SP I is the screening phase. Patients will sign an informed consent document prior to completing any study-related screening procedures. SP I is the time from Visit (V)1 to V2. The minimum timeframe for SP1 needs to allow sufficient time for patients to washout of any excluded medications and to review subject eligibility. Visit 1 will be considered complete when the last procedure of the screening assessment for the patient is completed. Once Study CGAR is open for enrollment, potentially eligible patients may enter screening directly from the parent study, CGAL or CGAM. If a patient is not experiencing cluster headache attacks (e.g., in remission) they may wait to enter screening for CGAR until they anticipate experiencing or are experiencing a cluster headache attack. If patients had completed the parent study, CGAL or CGAM, prior to Study CGAR being open for enrollment, potentially eligible patients may still enter screening for Study CGAR. Study procedures for V1 (Event List A) of Study CGAR will be completed as follows:

- If the last visit of the parent study is also the first visit of Study CGAR, then electrocardiograms (ECGs), vitals, weight, hematology, clinical chemistry, urinalysis, hemoglobin A1C (HbA_{1C}), and serum pregnancy, C-SSRS, and Self-Harm Supplement Form/ Self-Harm Follow-up Form (SHSF/SHFU) from the last visit of the parent study will also be used for the first visit of Study CGAR.
- If the last visit of the parent study is ≤ 2 weeks from V1 of Study CGAR, the hematology, chemistry, HbA_{1C}, and urinalysis do not need to be repeated.
- If the last visit of the parent study is > 2 weeks from V1 of Study CGAR, all study procedures in Event List A need to be completed at the first visit of Study CGAR.

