5.3. End of Study Definition

The study will continue in a specific region until any one of the following criteria is met:

- Sponsor decision
- Nonapproval from a regulatory agency in the country/region in which the patient is enrolled

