8.1. Discontinuation from Study Treatment

All patients are free to withdraw from participation in this study at any time and for whatever reason, specified or unspecified, and without prejudice.

Patients who discontinue early from the study should complete study procedures listed in Event List F in the Schedule of Activities.

8.1.1. *Temporary Discontinuation from Study Treatment*

This protocol allows for temporary interruption of treatment, based on clinical symptoms of efficacy and response as judged by the investigator (Section 5.1). Dosing in this scenario may be re-initiated at the study investigator's discretion. If dosing is temporarily interrupted due to a potential safety concern, dosing may be re-initiated at the study investigator's discretion following a discussion and agreement between the study investigator and Lilly Medical that re-initiation of dosing is appropriate.

8.1.2. *Discontinuation of Inadvertently Enrolled*

If the sponsor or investigator identify a patient who did not meet enrollment criteria and was inadvertently enrolled, a discussion must occur between the sponsor CRP and the investigator to determine if the patient may continue in the study. If both agree it is medically appropriate to continue, the investigator must obtain documented approval from the sponsor CRP to allow the inadvertently enrolled patient to continue in the study with or without treatment with investigational product.

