9.2. Adverse Events

Investigators are responsible for monitoring the safety of patients who have entered this study and for alerting Lilly or its designee to any event that seems unusual, even if this event may be considered an unanticipated benefit to the patient.

The investigator is responsible for the appropriate medical care of patients during the study.

Investigators must document their review of each laboratory safety report.

The investigator remains responsible for following, through an appropriate health care option, AEs that are serious or otherwise medically important, considered related to the investigational product or the study, or that caused the patient to discontinue the investigational product before completing the study. The patient should be followed until the event resolves, stabilizes with appropriate diagnostic evaluation, or is reasonably explained. The frequency of follow-up evaluations of the AE is left to the discretion of the investigator.

Lack of drug effect is not an AE in clinical studies, because the purpose of the clinical study is to establish treatment effect.

After the informed consent form (ICF) is signed, study site personnel will record via eCRF the occurrence and nature of each patient's pre-existing conditions, including clinically significant signs and symptoms of the disease under treatment in the study. In addition, site personnel will record any change in the condition(s) and any new conditions as AEs. Investigators should

record their assessment of the potential relatedness of each AE to protocol procedure, investigational product, via eCRF.

The investigator will interpret and document whether or not an AE has a reasonable possibility of being related to investigational product, study device, or a study procedure, taking into account the disease, concomitant treatment or pathologies.

A “reasonable possibility” means that there is a cause and effect relationship between the investigational product, study device and/or study procedure and the AE.

The investigator answers yes/no when making this assessment.

Planned surgeries and nonsurgical interventions should not be reported as AEs unless the underlying medical condition has worsened during the course of the study.

If a patient’s investigational product is discontinued as a result of an AE, study site personnel must report this to Lilly or its designee via eCRF clarifying if possible, the circumstances leading to discontinuations of treatment.

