10.3.2. Treatment Analyses

10.3.2.1. Patient Disposition

All patients who discontinue from the study will be identified, and the extent of their participation in the study will be reported. If known, a reason for their discontinuation will be given.

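### Discontinuation is reported only as a crude percentage over open-ended, unequal follow-up, so it cannot be read as a rate or compared across locks or studies

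*SAP*

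**What the plan says.** Protocol Section 4 (Table 4.1) sets the secondary objective "To characterize the reasons for discontinuation and AEs of interest for galcanezumab" and gives discontinuation rates as its endpoint, with no estimator, time point or denominator. SAP 4.2 repeats the objective. SAP 5.8 supplies the analysis: "The number and percentage of GMB-treated patients who discontinue early will be tabulated along with reasons for discontinuation", plus a listing of reasons by investigator.

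Three features of the design govern how long a patient can be observed:

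- Protocol 5.3: "The study will continue in a specific region until any one of the following criteria is met". The criteria are a sponsor decision or regulatory non-approval, and no duration is stated.
- Protocol 5.1, on patients in remission: "they may wait to enter screening for CGAR until they anticipate experiencing or are experiencing a cluster headache attack".
- Protocol 3.1: "some patients may receive monthly long-term treatment with galcanezumab for a period of months or years during the study".

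Protocol 10.3.2.1 adds, for those who leave: "All patients who discontinue from the study will be identified, and the extent of their participation in the study will be reported". SAP 5.8 does not repeat this. SAP 5.11 summarises exposure as a count of monthly doses, with a dated listing by patient. SAP 5.17 reports disposition at two interim locks (cutoffs 27 March 2018 and 4 September 2018) and again at the final lock.

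**The concern.** A rate needs a time base, and the planned figure has none. When patients are watched for very different lengths of time, the share who have left reflects both how fast they leave and how long they could be observed. Because disposition is reported at three successive locks, the percentage will tend to grow from one to the next simply because time has passed. A reader could take that growth for worsening tolerability, or set the final figure beside a study of fixed length and draw the wrong conclusion. In a long-term, single-arm safety study, how quickly and why patients stop is one of the main things a reader wants to know.

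**Working it through.** The documents state no sample size, dropout assumption or discontinuation figure, so there is no planned number to reproduce. The check asks how much the percentage moves when only follow-up changes.

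**1. Dependence on follow-up.** Assume a constant hazard h per patient-year and equal potential follow-up of t years. The expected crude percentage is 100 × (1 − exp(−h·t)). For example, h = 0.2 and t = 4 gives 1 − exp(−0.8) = 55.1%. The hazards are assumed values.

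| h | 6 months | 12 months | 24 months | 48 months |
|---|---|---|---|---|
| 0.1 | 4.9% | 9.5% | 18.1% | 33.0% |
| 0.2 | 9.5% | 18.1% | 33.0% | 55.1% |
| 0.4 | 18.1% | 33.0% | 55.1% | 79.8% |

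The ordering can reverse: a hazard of 0.1 followed for 48 months shows 33.0%, while a hazard four times as high followed for 6 months shows 18.1%.

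**2. The same percentage, different rates.** Solving h = −ln(1 − p)/t for p = 30%: −ln(0.7)/0.5 = 0.71 per patient-year if everyone could be followed for 6 months, and −ln(0.7)/4 = 0.09 if everyone could be followed for 48 months.

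**3. Calendar limits at each lock.** SAP Section 3 says version 1 was approved on 12 July 2016, before the first patient visit. From that date the longest possible follow-up is 623 days (20.5 months) at the first cutoff and 784 days (25.8 months) at the second. By the approval date on the current SAP, 2 March 2021, it is 1,694 days (55.7 months). The last patient visit is not stated, so 55.7 months is only an assumed upper end. For a patient with that maximum follow-up:

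| h | 20.5 months | 25.8 months | 55.7 months |
|---|---|---|---|
| 0.1 | 15.7% | 19.3% | 37.1% |
| 0.2 | 28.9% | 34.9% | 60.5% |
| 0.4 | 49.5% | 57.7% | 84.4% |

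The hazard is unchanged along each row.

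**4. Unequal follow-up in one study.** Suppose half the patients can be followed for 6 months and half for 48. With h = 0.2 the crude percentage is 0.5 × 9.5% + 0.5 × 55.1% = 32.3%. Expected person-time per patient is 0.5 × (1 − exp(−0.1))/0.2 + 0.5 × (1 − exp(−0.8))/0.2 = 1.61 years, and 0.323/1.61 = 0.2 per patient-year. With h = 0.1 and 0.4 the crude figures are 18.9% and 49.0%, while events per patient-year again return 0.1 and 0.4. This recovery follows from the constant-hazard assumption.

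**5. Does another output supply the time base?** Dose counts do not, because patients may stay in the study undosed. The protocol's extent-of-participation report covers those who leave, not those who stay, and its form is unspecified. Neither gives person-time for all treated patients.

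**The case against.** The strongest reply is that the objective is to characterise reasons, in a single-arm descriptive study with no powered comparison. A table and a listing by reason do that, and SAP 5.8 plans no contrast between locks or with other studies. This stands, and it limits the point to what the percentage can be used for. It does not supply a time base for an endpoint named as a rate.

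Several stronger readings are tempting, but the documents do not support them:

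- A reader might infer that the percentage is uninterpretable. It is a valid proportion of treated patients observed to leave, broken down by reason.
- A reader might infer that early has no meaning without a fixed duration. Protocol 8.2 lets patients continue until the end of study in Section 5.3, so early can be read as before that end. The end differs by region, but it is a reference point.
- A reader might infer that regional closure is pooled with patient-driven exits. Nothing says so. Closure is most naturally study end, and any closure coded as a discontinuation would appear under its own reason.
- A reader might infer that safety-related stops are lost. Protocol 8.1.1 does allow a patient to stay while dosing is paused: "If dosing is temporarily interrupted due to a potential safety concern, dosing may be re-initiated". But a temporary pause is not a discontinuation, so leaving it out is consistent with the endpoint. Protocol 9.2 requires eCRF reporting when a patient's "investigational product is discontinued as a result of an AE", and SAP 5.16 plans a table of AEs leading to discontinuation, also reported at both interim locks. Whether that table means leaving treatment or leaving the study is not stated, so omission is not shown.

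The follow-up spread is also unknown. The arithmetic shows how the measure behaves, not how far this trial's figure is distorted.

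**Conclusion.** The point holds in a limited form. As planned, the secondary endpoint is a correct description of who left and why. It cannot serve as a rate or be compared across the two interim locks, the final lock or other studies. Under constant assumed hazards of 0.1 to 0.4 per patient-year, the crude figure runs from about 5–18% at 6 months to 33–80% at 4 years. Its dependence on follow-up does not rest on any one hazard; the size of the effect here does rest on the hazards and on a follow-up distribution that the documents do not give. This is an inexpensive improvement worth making. The meaning of discontinuation in the AE table and the handling of dosing pauses are secondary clarifications.

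**What to change.** Keep the SAP 5.8 table and listing. For the GMB-treated population, add:

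- total patient-years from first dose to study discontinuation or closure, with discontinuations per 100 patient-years overall and by reason;
- a Kaplan-Meier estimate of time from first dose to study discontinuation at fixed times such as 6, 12 and 24 months, censoring patients still in the study at sponsor or regional closure. If the hazard changes over time, a single rate per patient-year averages over it, so the fixed-time estimates are the safer basis for comparison;
- for individual reasons, cumulative incidence treating the other reasons as competing events.

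As clarifications, state whether AEs leading to discontinuation refers to treatment or study. Count safety-related dosing interruptions in patients who remain in the study as a separate row, if the reason was captured.

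The cost is one extra table or figure, from entry, exit and dosing dates that the trial should already hold. SAP 5.4 allows such a change to be described in the SAP or study report without a protocol amendment, provided no principal feature of the protocol changes. No clinical stopping or re-initiation rule is affected.

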5.9. Important Protocol Deviations

Summary and listing of subjects with important protocol deviations will be provided for the GMB-treated population.

Section 7 ([Appendix 1](#)) lists the categories, subcategories, study specific terms of important protocol deviations, and source of identification. Per study team's discretion, for non-programmable protocol deviation, additional categories and subcategories other than the ones in Appendix 1 can always be added into the final nonprogrammable protocol deviations list as deemed necessary.

5.10. Patient Characteristics

The following patient characteristics at baseline will be summarized for all GMB-treated patients:

- Demographics (age, gender, race, ethnicity, height, weight, body mass index, country, region)
Note: Age, gender, race, and ethnicity will be based upon the information from the parent trial.
- Baseline disease characteristics:
 - number of cluster headache attacks yesterday
 - mean pain severity of cluster headache attacks yesterday
 - mean duration of cluster headache attacks yesterday
 - was abortive treatment used?

Pre-existing conditions will be summarized. Pre-existing conditions are medical events ongoing at the time of informed consent.

Note: The reference to yesterday defines a 24-hour period from midnight to midnight the day before the assessment date.

5.11. Treatment Exposure and Compliance

This open-label study dosing will be based upon the study investigator's judgment and there will not be any formal computation of treatment compliance. Total number of monthly doses administered will be summarized for the GMB-treated population. Treatment received will also be reported in an individual subject listing by providing the date, time, and the injection dose administered.

5.12. Concomitant Therapy

The proportion of patients who receive concomitant medication will be summarized using the WHODRUG dictionary preferred term (PT) and will be presented in the order of decreasing frequency of usage. If there are different PTs for salt forms of a preventive or abortive medication, these PTs will be combined for the medication in the presentation. Concomitant therapies are those that started on or continued after the date of first dose of study medication. All records will be used in the above summary even if frequency, dose, or dates of use are missing.

5.13. Efficacy Analyses

Descriptive summaries of the PGI-I, a 7-point scale, with 1=very much better and 7=very much worse (Guy 1976) will be presented at each time point collected during postbaseline, as described in the schedule of activities. It will be summarized as both a categorical and continuous variable.

The proportion of patients reporting a score of 1 ("very much better") or 2 ("much better") on the PGI-I 1 month after receiving their first dose will be reported.

